9.5 Everolimus dose modifications and treatment interruptions/discontinuation guidelines

- Renal impairment: No dose adjustment necessary.
- Hepatic impairment: If total bilirubin $> 2 \text{ mg/dL}$, hold treatment for up to 4 weeks, then reduce dose to 5 mg PO daily once total bilirubin $\leq 2 \text{ mg/dL}$.
- Everolimus will be held for any grade 3 hematologic adverse event, grade 2 pulmonary toxicity or any other grade 3 non-hematologic toxicity, excluding hyperlipidemia.

- If recovery (grade 2 or less for hematologic or non-hematologic toxicities) occurs within 4 weeks, everolimus will be resumed at a reduced dose of 5 mg PO daily.
- Any grade ≥ 3 pulmonary toxicity occurring at any time during therapy warrants discontinuation of everolimus and the study chair should be contacted.
- If BSA changes by $> 10\%$ at any time during the study, the dose of everolimus must be adjusted if needed and accordingly.
- Everolimus will not be reduced below 5mg.
- Everolimus may be held for a maximum of 4 weeks from the scheduled date of cycle commencement to permit recovery from toxicities/adverse events as outlined above. If more than 4 weeks are required for recovery, the study chair may allow continuation of everolimus pending the approval of the local IRB.

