Dual aromatase and mTOR inhibition was evaluated in a phase I trial of letrozole at the standard dose of 2.5 mg PO QD, with two different dose levels of everolimus at 5 mg PO QD or 10 mg PO QD [120]. Safety and pharmacokinetic studies revealed the combination to be safe, with no major interactions at either dose level of everolimus. Only one dose-limiting toxicity, grade 3 thrombocytopenia, occurred in the everolimus 10 mg PO QD cohort. A randomized phase II neoadjuvant breast cancer trial of letrozole 2.5 mg PO QD plus everolimus 10mg PO QD or placebo also reported an acceptable toxicity profile for the combination, with grade 3/4 toxicities occurring in $\leq 5\%$ of patients receiving everolimus [122]. This included three patients who developed pneumonitis which resolved within two weeks of everolimus discontinuation.

EVOLVE-1 is a phase III trial of everolimus at 7.5 mg PO QD versus best supportive care in advanced typical HCC following failure/intolerance of sorafenib (www.clinicaltrials.gov, NCT01035229). The reduced dose of 7.5 mg PO QD was chosen given concerns about pneumonitis at the 10 mg PO QD dose, particularly in a patient population with abnormal hepatic drug clearance. Although most patients with FLL-HCC have normal hepatic parenchyma, hepatic reserve may be somewhat impaired by the presence of tumor. Thus, for the purpose of this trial, everolimus 7.5 mg PO QD will be administered.

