- If everolimus or both EDT drugs must be completely discontinued, patient will be declared off trial. However, if a patient is able to tolerate either component of combined therapy (ie. Everolimus or EDT) but not both, and is experiencing clinical benefit, the study chair may allow continuation of everolimus or EDT pending the approval of the local IRB.
- Treatment will continue until disease progression, global clinical deterioration, unacceptable toxicity and/or consent withdrawal.
- Therapy may be held for a maximum of 4 weeks to recover from toxicity (see Sections 9.5 through 9.8)

9.4 Part 2: Combined therapy with everolimus and EDT after progression on either everolimus or EDT alone

- Patients who develop disease progression on either Arm A or B during Part 1 of the study will proceed to combined therapy.
 - At the start of Part 2 the last CT scan on Part I will be used as the baseline scan for RECIST 1.1 criteria.

Patients who were on everolimus (Arm A) during Part 1 will begin EDT with leuprolide 7.5 mg IM .

- Patients who required a dose reduction on Arm A during Part 1 will continue at the reduced dose level for Part 2.
- Day 1 of Cycle 1: Baseline serum estrone, estradiol, testosterone and follicle-stimulating hormone (FSH) level in all patients. If estradiol is within postmenopausal range for women (≤ 30 pg/mL) and testosterone is within the castration range for men (≤ 50 ng/dL), the patient does not have to have hormones retested at week 2 and maybe begin letrozole 2.5 mg po QD Week 2 of Cycle 1.
 - Week 2 of Cycle 1 (+/- 7 days): Women with estradiol not within postmenopausal range (≤ 30 pg/mL) or men with testosterone not within the castration range measure serum estradiol and testosterone; if estradiol is within postmenopausal range (women) or testosterone is within the castration range (men), begin letrozole 2.5 mg po QD. Otherwise, retest hormones on C2W1. Consult MSKCC PI if hormones are still not within range. to further discuss the letrozole start date.
 - Leuprolide 7.5 mg IM will be administered every 4 weeks (+/- 7 days).

Patients who were on EDT (Arm B) during Part 1 will begin everolimus on Day 1 of Part 2 of the study at the following doses:

- Patients with a BSA $\leq 1.5 \text{ m}^2$ will receive everolimus 5 mg PO QD.
- Patients with a BSA $> 1.5 \text{ m}^2$ will receive everolimus 7.5 mg PO QD.
- Patients should continue with their every 12 weeks hormone testing schedule from Arm B.

All Patients on Part II

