- Patients will undergo clinical and laboratory evaluations on weeks 1, 2 and 3 of Cycle 1. For all subsequent cycles starting with Cycle 2, evaluations will take place on weeks 1 and 3.
- Only clinical and laboratory assessments performed at Memorial Sloan Kettering Cancer Center or participating sites will be used to determine if patient will proceed with protocol treatment using the parameters listed below. Protocol assessments performed at a local oncologist may be used to determine treatment decisions at discretion of treating investigator and local oncologist.
- Before treatment on week 1 and 3 of each cycle: CBC and differential, comprehensive metabolic panel (Na, K, Cl, HCO₃, BUN, creatinine, AST, ALT, alkaline phosphatase, glucose), LDH, calcium, phosphorus, albumin, bilirubin, PT/INR, and ammonia. Treatment will only proceed if:
 - Hematologic: ANC $\geq 1.0 \times 10^9/L$, platelets $\geq 50 \times 10^9/L$
 - Renal: creatinine $\leq 2 \times$ upper limit of normal or creatinine Clearance of $\geq 60 \text{ cc/mL}/1.73 \text{ m}^2$ for patients > 16 years old. For patients ≤ 16 years of age, creatinine Clearance of $\geq 70 \text{ cc/mL}/1.73 \text{ m}^2$ or serum creatinine based on the following chart:

Creatinine clearance or radioisotope GFR $\geq 70 \text{ ml/min}/1.73 \text{ m}^2$ or serum creatinine based on age/gender as follows:

Age	Maximum Serum Creatinine (mg/dL)	
	Male	Female
10 to < 13 years	1.2	1.2
13 to < 16 years	1.5	1.4
≥ 16 years	1.7	1.4

The threshold creatinine values in this Table were derived from the Schwartz formula for estimating GFR (Schwartz et al. J. Peds, 106:522, 1985) utilizing child length and stature data published by the CDC.

- Hepatic: total bilirubin $\leq 2 \text{ mg/dL}$, alanine and aminotransferase levels $\leq 5 \times$ upper limit of normal for age.
- If hematologic, renal and hepatic function criteria are not met, treatment will be held and the patient will be reassessed weekly. Please refer to section 11.0 Toxicities/Side Effects for the

management of other adverse events during therapy.

- Fasting blood glucose and fasting lipid profile (total cholesterol, triglycerides, LDL, HDL) will be drawn on week 1 of each cycle beginning with cycle 2.
- Past FLL-HCC patients have also been referred for psychiatric services with depressive symptoms, immaturity and suicidal ideation as the most commonly observed symptoms. Participants on study will be psychiatrically evaluated as clinically indicated.

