11.2 Anticipated adverse events

- Everolimus:

- Likely: stomatitis, xerostomia, nausea/vomiting, diarrhea, anemia, leucopenia, thrombocytopenia, increased transaminases, fatigue, dysglycemia, hyperlipidemia, hypophosphatemia, low bicarbonate, upper respiratory symptoms or infection, asthenia, peripheral edema, epistaxis, pruritus
- Less likely: rash, , dysgeusia, anorexia, weight loss, pneumonitis, dyspepsia, arthralgia, myalgia, hyperkalemia, hyponatremia, hypomagnesemia, hand-foot syndrome
- Rare but serious adverse events: chest pain, cardiac arrhythmias, cardiac arrest, pancreatitis, renal failure, a secondary malignancy, diabetes, bleeding and hepatitis B reactivation

- Letrozole:

- Likely: hot flashes, edema, hyperlipidemia, arthralgia, weakness, decreased bone mineral density, night sweats, headache, fatigue, dizziness, constipation, weight loss or gain, back pain, dyspnea, chest pain, nausea, vomiting, vaginal bleeding, renal failure, infection
- Less likely: cough, hypertension, diarrhea, anorexia, breast tenderness/soreness
- Rare but serious adverse events: cerebrovascular accident, venous thrombosis, myocardial infarction, and secondary malignancies

- Leuprolide:

- Likely: hot flashes, headache, depressed mood, pain or bruising at injection site, hyperhidrosis, insomnia, decreased bone mineral density, edema, hyperlipidemia, weight gain or loss, decreased libido, hypogonadism, acne, breast tenderness/soreness, breast enlargement, dysglycemia, hyperuricemia, infection at injection site, paresthesias, erectile dysfunction, pelvic or urinary tract discomfort
- Less likely: nausea, vomiting, dizziness, fatigue, arthralgia, myalgia, epistaxis, osteoporosis
- Rare but serious adverse events: chest pain, arrhythmia, thrombosis, fever, seizure, renal failure, hypersensitivity reaction, hemoptysis, hepatic failure

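### Section 9.5 holds everolimus for grade 2 pulmonary toxicity but counts grade 2 as recovered, so a pulmonary hold meets its restart test as soon as it begins

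*Combined protocol and SAP*

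**What the plan says.** Section 9.5 of the protocol sets three rules for everolimus toxicity.

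- **Hold:** "Everolimus will be held for any grade 3 hematologic adverse event, grade 2 pulmonary toxicity or any other grade 3 non-hematologic toxicity", with hyperlipidemia excepted.
- **Restart:** "If recovery (grade 2 or less for hematologic or non-hematologic toxicities) occurs within 4 weeks, everolimus will be resumed at a reduced dose". The restart dose is 5 mg daily.
- **Stop:** for grade 3 or higher, "pulmonary toxicity occurring at any time during therapy warrants discontinuation of everolimus and the study chair should be contacted".

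The section also sets a dose floor: "Everolimus will not be reduced below 5mg". A hold may last at most 4 weeks, unless the study chair allows continuation with local IRB approval.

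Section 9.8, on combined therapy, repeats the grade 2 pulmonary trigger when it allows EDT to continue during an everolimus interruption. It gives no restart grade. The criteria in section 10 for proceeding with treatment at weeks 1 and 3 cover hematologic, renal and hepatic function. For other adverse events the reader is sent on: "Please refer to section 11.0 Toxicities/Side Effects for the" management. Section 11.2 names pneumonitis among the less likely everolimus effects ("weight loss, pneumonitis, dyspepsia, arthralgia, myalgia, hyperkalemia"), but section 11 gives no instruction for managing it.

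**The concern.** A hold-and-restart rule works only if the restart grade is lower than the grade that triggered the hold. The authors singled out pulmonary toxicity for an earlier hold than any other class, yet applied the shared restart threshold to it. The earlier hold then has no improvement to wait for.

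This is a patient-safety matter. Section 3.8 explains that the cited phase III trial in typical HCC used 7.5 mg because of concern about pneumonitis at 10 mg, and this trial adopts 7.5 mg. The same section describes a randomized neoadjuvant trial of letrozole with everolimus 10 mg or placebo, and says of the toxicity in the everolimus group: "This included three patients who developed pneumonitis which resolved within two weeks of everolimus discontinuation". Everolimus with letrozole is part of the regimen in Arm C and Part 2.

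**Working it through.** No sample size or error rate is involved. The check sets the section 9.5 grades side by side.

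**Step 1: does the restart rule cover pulmonary toxicity?** Yes. The hold sentence lists grade 2 pulmonary toxicity and then any *other* grade 3 non-hematologic toxicity, which places pulmonary events among the non-hematologic ones. The restart rule applies to hematologic and non-hematologic toxicities alike, with no exception.

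**Step 2: compare hold and restart grades.**

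| Toxicity | Held at | Counted as recovered | Restart test when the hold begins |
|---|---|---|---|
| Pulmonary | grade 2 (3 or higher: discontinue) | grade 2 or less | already met |
| Hematologic | grade 3 | grade 2 or less | not met; needs at least one grade of improvement |
| Other non-hematologic, excluding hyperlipidemia | grade 3 | grade 2 or less | not met; needs at least one grade of improvement |

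Pulmonary grade 1 is not held, and grade 3 or higher is not resumed. The hold therefore governs one pulmonary grade, and that grade passes the restart test. The 4-week recovery window does nothing for pulmonary events.

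**Step 3: look for a restart grade elsewhere.** Sections 9.1 to 9.4, 9.8, 10, 11 and 13 contain none. Pulmonary function tests appear in the section 10 schedule only as clinically indicated.

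**Step 4: dose on restart.**

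- Patient on 7.5 mg: 1 − 5/7.5 = 33.3% reduction.
- Patient on 5 mg: 1 − 5/5 = 0% reduction.

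The second group comprises patients with BSA below 1.5 m² (sections 9.1 and 9.3) and anyone reduced earlier. Section 9.4 carries the latter into Part 2: "Patients who required a dose reduction on Arm A during Part 1 will continue at the reduced dose level for Part 2".

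**The case against.** The strongest reply is that recovery ordinarily means improvement from the event that caused the hold. Section 9.5 says the hold exists to allow recovery, and a reading that ends a mandatory hold as it starts makes the trigger pointless. On this view, a parenthesis written for the grade 3 triggers was simply not adapted to the one grade 2 trigger, and clinicians would not apply it literally. There are also general safeguards: therapy stops for unacceptable toxicity or on the investigator's judgment (section 13), adverse events are assessed repeatedly (section 10), and toxicity is discussed on roughly monthly calls (section 16.1).

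Part of this stands. Many investigators would wait, and the safeguards make re-exposure during active pneumonitis less likely than the bare text suggests. But the parenthesis defines recovery by grade and makes no pulmonary exception, and the restart that follows is directive. Even if improvement is implied, the text does not say to what grade, so sites could differ. None of the safeguards sets a restart threshold.

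Two further objections are fair. The documents give no source for grade 1 as the threshold, so the value is the sponsor's to set. And the 5 mg restart dose needs no clarification, because the stated restart dose and the floor together fix it.

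**Conclusion.** The concern holds. As written, the pulmonary restart criterion is met at the start of every pulmonary hold, while the same criterion works for the toxicities held at grade 3. This is a stated safety rule that gives the wrong result when followed, so it should be corrected.

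Its reach is grade 2 pulmonary events in patients taking everolimus in Arms A and C and in Part 2. How many such events to expect cannot be derived from the documents. Discontinuation at grade 3 or higher and the one-third dose cut for patients on 7.5 mg limit the harm; patients already on 5 mg have only the first protection. The conclusion rests on reading the parenthesis as the definition of recovery. No effect on PFS6 or the operating characteristics is claimed.

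**What to change.** Add one sentence to section 9.5 giving pulmonary toxicity its own recovery threshold below the hold trigger, for example: *for pulmonary toxicity, recovery means grade 1 or less*. Leave the existing threshold for the toxicities held at grade 3.

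The change needs no extra procedures or patients. Its cost is somewhat longer holds for grade 2 pulmonary events. A hold unresolved at 4 weeks would go through the existing study-chair and local IRB exception (sections 9.5 and 13). The three pneumonitis cases in section 3.8 resolved within two weeks of stopping everolimus, inside that window, although three cases are few.

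The same amendment could tidy one editorial point: section 9.8 refers to grade 2 hematologic events where section 9.5 holds at grade 3. Aligning 9.8 with 9.5 removes the mismatch.

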9.6 Letrozole dose modifications and treatment interruptions guidelines

If total bilirubin $> 3\text{mg/dL}$, hold treatment for up to 4 weeks, once total bilirubin $\leq 3\text{mg/dL}$, continue letrozole at 2.5 mg PO QD every other day.

Otherwise no modifications required.

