9.7 Leuprolide dose modifications guidelines

No dose modifications required.

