13.0 CRITERIA FOR REMOVAL FROM STUDY

Study therapy will continue until/unless there is:

[figure not shown]
- Disease progression as defined by RECIST 1.1 criteria
- Clinical progression
- Unacceptable toxicity
- Patient withdrawal of consent
- Patient noncompliance
- Intercurrent illness that prevents further administration of treatment. Inability to take EDT and everolimus simultaneously for patients who receive combination therapy. In very special circumstances, study chair may allow continuation of everolimus or EDT pending the approval of the local IRB.
- General or specific changes in the patient’s condition rendering him/her unacceptable for further treatment in the judgment of the investigator. Delay of therapy for > 4 weeks. If more than 4 weeks are required for recovery, the study chair may allow continuation of everolimus or EDT pending the approval of the local IRB.
- Patients who are removed from the study for any of the above reasons will continue to be monitored for survival every 3 months unless consent for continued follow-up is withdrawn.

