14.0 BIOSTATISTICS

Primary efficacy endpoints for Part 1 of protocol

- The primary efficacy endpoints for Part 1 of the study is progression-free survival at 6 months (PFS6).
- A progression event refers to the first evidence of radiographic disease progression, clinical progression as determined by study investigators, or death.
- Imaging performed in 6 months will be used to determine PFS6.
- PFS6 will be defined as the percentage of patients who are alive and have not experienced a progression event as defined above at 6 months from the date that study therapy was initiated. Patients that come off study before the 6 months scan will be considered events for the primary endpoint analysis.
- PFS6 will be assessed using a Simon's minimax two stage design, hypothesizing an improvement in PFS6 from 40% to 64% with the study regimen. Sixteen patients will be enrolled onto each of Arms A, B and C for a total of 48 patients in the first stage. Accrual will stop till the progression status at 6 months is obtained on all 16 patients in each arm. If 6 or less patients in one arm are progression free at 6 months the regimen in that arm will be terminated; otherwise, if 7 or more patients are alive and progression free at 6 months, enrollment will be extended in that arm to 28 patients (maximum total of 84 patients). At the end of stage 2, the respective regimens will be declared promising if 15 or more of the 28 patients in each arm are alive and progression free at 6 months. The design assumes a type I error (falsely accepting a non-promising therapy) and type II error (falsely rejecting a promising therapy) both set to 10%.

Figure 4: Simon's minimax 2 stage design (schematic applicable for each study arm)

- The probability of early termination due to drug inefficacy is 53%. In the event that 2 or more arms show promising activity, we will use the “pick the winner” format based on the randomized phase II clinical trials approach proposed by Simon et al. In this case, the regimen that has at least 15 patients progression free at 6 months and exceeds by at least 2 patients the number of progression free patients in the second best arm would be declared the winner. The probability of selecting the better regimen is 85%; the probability that no regimen is selected is 7%, while the probability of a tie is approximately 6% [149].

Secondary endpoints

- Secondary endpoints are:
 - Median PFS
 - Median overall survival (OS)

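### For total bilirubin above 2 and up to 3 mg/dL, Section 10 holds all treatment while Section 9.6 continues letrozole unchanged, and no section says which governs

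*Combined protocol and SAP*

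**What the plan says.** **Section 10 (summary of the evaluation plan during treatment).** At weeks 1 and 3 of each cycle, treatment goes ahead only if the laboratory criteria are met, among them a total bilirubin no higher than 2 mg/dL. Otherwise: "If hematologic, renal and hepatic function criteria are not met, treatment will be held and the patient will be reassessed weekly". No arm or drug is named.

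**Section 9.6 (letrozole).** "If total bilirubin $> 3\text{mg/dL}$, hold treatment for up to 4 weeks". Once bilirubin is 3 mg/dL or lower, the instruction is to "continue letrozole at 2.5 mg PO QD every other day". In all other cases the section asks for no change.

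**Section 9.2 (Arm B).** EDT can be held for at most 4 weeks for toxicity, and the reader is sent to Sections 9.6 and 9.7, not to Section 10.

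**Section 9.5 (everolimus).** The hold starts above 2 mg/dL, the same limit as in Section 10.

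**Section 13.** The removal criteria include "Delay of therapy for > 4 weeks". The next sentence lets the study chair permit everolimus or EDT to go on after a longer recovery if the local IRB agrees.

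**Section 14.** "Patients that come off study before the 6 months scan will be considered events for the primary endpoint analysis".

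**The concern.** A site treating an Arm B patient whose bilirubin is, say, 2.5 mg/dL has two instructions. Section 10 tells it to hold treatment and recheck weekly. Section 9.6 tells it to carry on with letrozole unchanged. Two sites that follow the protocol carefully can treat the same patient differently.

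The band is within easy reach. Section 6 admits patients up to exactly 2 mg/dL, and Section 3.8 notes that tumor may impair hepatic reserve.

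If letrozole is held and later restarted under Section 9.6, the schedule cannot be carried out as written, because it says both once daily and every other day.

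Patient care is the first thing at stake. The second is the primary endpoint: a long hold can lead to removal, and early removal is scored as a PFS6 event. The two bilirubin rules can therefore, in some circumstances, give the same patient different endpoint results.

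**Working it through.** **1. The two rules side by side**

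| Total bilirubin (mg/dL) | Section 10, all treatment | Section 9.6, letrozole | Consistent? |
|---|---|---|---|
| 2 or less | proceeds | no change | yes |
| above 2 to 3, never higher | held, weekly recheck | no change | **no** |
| above 3 | held | held, up to 4 weeks | yes |
| back from above 3 to the 2–3 band | still held | resumed | **no** |
| back from above 3 to 2 or less | may resume | resumed | yes |

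Both the hold trigger and the resume trigger differ.

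**2. Does the choice of drug explain it?** For everolimus, Sections 9.5 and 10 agree at 2 mg/dL. Arm B receives no everolimus, and Section 10 does not limit its criteria to everolimus. For other adverse events Section 10 refers to Section 11. It does not defer to Sections 9.5 to 9.8.

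**3. Which arms can see a different PFS6 result?**
- Arm A: no letrozole, so no conflict.
- Arm C: the letrozole instructions conflict, but everolimus is held above 2 mg/dL under both sections, so the delay for that drug is the same either way.
- Part 2: these patients have already progressed, so their Part 1 PFS6 status is settled.
- Arm B: a different result is possible. It needs all of the following: bilirubin above 2 mg/dL for more than 4 weeks; no stay above 3 mg/dL long enough to cause the same removal under Section 9.6; no study chair exception; off study before the 6-month scan; and no radiographic or clinical progression or death by 6 months, which would be an event under either rule.

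**4. The design this would feed into.** Inputs from Section 14, per arm: PFS6 of 40% against 64%; stop if 6 or fewer of 16 are progression free; promising if 15 or more of 28; both error rates set to 10%; early termination probability 53%.

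With X1 ~ Bin(16, p) and X2 ~ Bin(12, p):
- P(stop early) = P(X1 ≤ 6)
- P(promising) = Σ over x = 7 to 16 of P(X1 = x) · P(X2 ≥ 15 − x)

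| | p = 0.40 | p = 0.64 |
|---|---|---|
| P(stop early) | 52.7% (plan: 53%) | 2.8% |
| P(promising) | 9.89% (limit 10%) | 90.19% (target 90%) |
| exactly 7 of 16 | 18.9% | 5.1% |
| exactly 15 of 28, having passed stage 1 | 5.0% | 7.5% |

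The plan's figures reproduce, with almost no slack. The last two rows are the chances that a count sits where one patient scored as an event instead of progression free would reverse the decision.

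**5. Illustration only.** Let f be the share of otherwise progression-free Arm B patients scored as events solely through this route. The documents give no value for f. Replace p by p(1 − f):

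| f | p = 0.64 becomes | P(promising) | p = 0.40 becomes | P(promising) |
|---|---|---|---|---|
| 0 | 0.640 | 90.2% | 0.400 | 9.9% |
| 2% | 0.627 | 87.5% | 0.392 | 8.4% |
| 5% | 0.608 | 82.6% | 0.380 | 6.6% |
| 10% | 0.576 | 72.4% | 0.360 | 4.2% |

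For scale, at 64% the expected number progression free is 0.64 × 28 = 17.9, so f = 5% is 0.05 × 17.9 = 0.9 of a patient.

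**The case against.** **The specific rule could be taken to override the general one.** Section 10 can be read as a general visit check and Section 9.6 as the letrozole rule, and Section 9.2 does send Arm B sites to Section 9.6. This is reasonable, but it is an inference. Section 10 sets a condition for treatment as a whole and makes no exception. A cautious site could just as well apply the stricter limit.

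**The renal and leuprolide statements do not add further contradictions.** A reader might infer that they do. Section 9.5 says "Renal impairment: No dose adjustment necessary" while Section 10 holds for renal criteria. However, the first concerns dose and the second concerns holding, and a drug can be held and restarted at the same dose. Section 9.5 itself treats holding and reducing as separate steps in its hepatic rule. Likewise "No dose modifications required" in Section 9.7 stands under a heading about dose modification only, whereas the headings of 9.5 and 9.6 also cover interruptions. Section 9.2 allows EDT to be held. At most, Section 9.7 is silent on when to hold leuprolide. This objection stands.

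**The route to the primary endpoint is long.** A reader might infer that a held patient becomes a PFS6 failure, or that every EDT patient in the band affects the primary analysis. The documents do not support either. A hold alone is not an event, the study chair can allow treatment to go on, and the several conditions must all occur together, in effect in Arm B only. This objection also stands.

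**Sensitivity to one patient is not specific to this defect.** Any misclassification at a boundary of a two-stage design has the same effect. That is correct. The boundary probabilities describe the design, not how often this conflict would matter.

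**Conclusion.** The protocol contradicts itself on letrozole for total bilirubin above 2 and up to 3 mg/dL, on both holding and resuming, and does not say which section prevails. The resumed letrozole schedule is also unworkable as written. Both follow from the text alone and need no assumption.

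The main weight lies on patient care: sites have conflicting instructions for patients on EDT. The effect on PFS6 is secondary, conditional and of unknown frequency, and essentially limited to Arm B. The power losses shown depend wholly on the assumed f. They indicate how sensitive the design is and should not be read as an estimate of harm. The plan's stated error rates are not in question, and the renal and leuprolide statements are not part of the finding.

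**What to change.** - Reconcile Sections 9.6 and 10, together with the cross-reference in Section 9.2, so that one stated rule gives the bilirubin trigger for holding and for resuming each drug. A single table by drug would do this.
- State which section governs if a general treatment criterion and a drug-specific rule differ.
- Rewrite the resumed letrozole schedule so that it gives one frequency.
- In the same edit, align the renal line in Section 9.5 and the leuprolide line in Section 9.7 with Section 10, making clear whether each concerns dose, holding or both.

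The thresholds and the schedule are for the sponsor's clinicians to decide. The cost is a protocol wording amendment with its IRB approvals. Sample size, decision rules and analysis do not change.
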